### **5.4.1. Data Handling**

Unless otherwise specified, data handling rules specified in Sections 5.2.2 will be applied to the secondary analyses.

### **5.4.2. EASI**

#### **5.4.2.1. Definition**

Refer to Section 5.3.1 for the definition of EASI score.

EASI-100 responder is defined as a 100% improvement from baseline in EASI total score (EASI score=0).

EASI-90 responder is defined as at least a 90% improvement from baseline in EASI total score.

EASI-75 responder is defined as at least a 75% improvement from baseline in EASI total score.

EASI-50 responder is defined as at least a 50% improvement from baseline in EASI total score.

#### **5.4.2.2. Analyses Related to EASI**

- The proportion of participants who achieve EASI-50, EASI-90, EASI-100 at Week 16 will be compared between each of the bermekimab group and the placebo group.
- The improvement from baseline in EASI total score at Week 16 will be compared between each bermekimab group and placebo group using a MMRM model including treatment group, visit, treatment group by visit interaction as factors, baseline EASI score, and baseline EASI score by visit interaction as covariates.
- The proportion of participants who achieve EASI-50, EASI-75, EASI-90, and EASI-100 will be summarized by treatment group over time. In addition, for participants who discontinued study treatment or have missing data, the proportion of participants who achieve EASI-75 through Week 16 will be analyzed utilizing the hypothetical estimand (i.e. MI method) and treatment policy estimand (i.e. observed data).
- The proportion of participants who achieve EASI-75 by baseline EASI severity will be summarized by treatment group over time through Week 16. In addition, a line plot displaying the proportions and 95% CIs for EASI-75 response through Week 16 by treatment group will be provided.
- The improvement from baseline and percent improvement from baseline in EASI total score will be summarized by treatment group over time.
- The proportion of subjects who achieve 100% improvement,  $\geq 90\%$ ,  $\geq 75\%$ , or  $\geq 50\%$  improvement from baseline in EASI component (Edema/Papulation, erythema, and Excoriation) and region component (neck/neck, trunk, upper extremities, and lower extremities) will be summarized over time by treatment group.

In addition, two supplementary analyses (a) improvement from baseline in EASI total score at Week 16, and (b) improvement from baseline and percent improvement from baseline in EASI total score over time will be performed with the following data handling rules:

- Data is considered as missing after the discontinuation of study intervention, missing data is handled through the MMRM model.

- Data will be analyzed based on observed data regardless of whether the subject discontinued treatment or have missing data.

### **5.4.3. Numerical Rating Scale (NRS) for Itch & Pain**

#### **5.4.3.1. Definition**

Patients will be given a diary to complete each night before bed. Patients will be asked to report “average pain”, and “worst moment pain” as well as “average itch” and “worst moment itch” on a 0-10 numeric rating scale. Patient diaries will be collected weekly. A higher score indicates more severe disease (0 indicate no itch or no pain). The baseline is defined as the average score of last 7 days prior to Week 0 study agent administration. If there are more than 3 days missing data, then baseline is set as missing. Missing baseline will not be imputed.

Seven daily NRS scores are averaged into a weekly score (ie 7 days [from day -7 to -1] prior to a visit). Four days out of 7 days (either consecutive or nonconsecutive) are necessary to derive a weekly score; otherwise data are considered missing for that week.

#### **5.4.3.2. Analyses Related to NRS**

- The improvement (reduction) from baseline in NRS score (weekly average overall pain, weekly average worst daily pain, weekly average overall Itch, weekly average worst daily Itch) at Week 16 will be compared between each bermekimab group and placebo group using a MMRM model.
- The proportion of participants who achieve  $\geq 4$ -point improvement (reduction) in NRS score (weekly average overall pain, weekly average worst daily pain, weekly average overall Itch, weekly average worst daily Itch) from baseline at Week 16 will be compared between each bermekimab group and placebo group using a CMH test stratified by baseline EASI severity in patients with baseline score  $\geq 4$ .
- The improvement (reduction) from baseline in NRS score (weekly average overall pain, weekly average worst daily pain, weekly average overall Itch, weekly average worst daily Itch) will be summarized by treatment group over time.
- The proportion of participants who achieve  $\geq 4$ -point improvement (reduction) in NRS score (weekly average overall pain, weekly average worst daily pain, weekly average overall Itch, weekly average worst daily Itch) from baseline will be summarized by treatment group over time in patients with baseline score  $\geq 4$ .

In addition, two supplementary analyses (a) improvement from baseline in NRS itch score at Week 16, and (b) improvement from baseline in NRS itch score over time will be performed with the following data handling rules:

- Data is considered as missing after the discontinuation of study intervention, missing data is handled through the MMRM model.

- Data will be analyzed based on observed data regardless of whether the subject discontinued treatment or have missing data.

#### **5.4.4. Investigators Global Assessment (IGA)**

##### **5.4.4.1. Definition**

The Investigator's Global Assessment (IGA) documents the investigator's assessment of severity of AD and clinical response to treatment based on a 5-point scale clear (0), almost clear (1), mild (2), moderate (3), or severe (4). A higher score indicates more severe disease

##### **5.4.4.2. Analyses Related to IGA**

- The proportion of subjects achieve an IGA score of clear (0), IGA score of clear (0) or almost clear (1), and IGA score of mild or better ( $\leq 2$ ) and at least 2 grade improvement from baseline at Week 16 will be compared between each of the bermekimab groups and the placebo group.
- The proportions of subjects who achieve an IGA score of clear (0) response, IGA score of clear (0) or almost clear (1) response, and IGA score of mild or better ( $\leq 2$ ) and at least 2 grade improvement from baseline response over time will be summarized by treatment group. In addition, supplementary analyses for the proportion of participants who achieve IGA responses through Week 16 will be performed utilizing the hypothetical estimand (i.e. MI method where appropriate using the similar method as for EASI-75) and treatment policy estimand (i.e. observed data).
- Line plots will be provided displaying the proportions and 95% CIs of subjects achieve an IGA score of clear (0); and an IGA score of clear (0) or almost clear (1) through Week 16 by treatment group.

#### **5.4.5. DLQI**

##### **5.4.5.1. Definition**

The DLQI is a dermatology-specific quality of life instrument designed to assess the impact of AD disease on a subject's quality of life. It is a simple response (0 to 3 where 0 is "not at all" and 3 is "very much") to 10-item questionnaire that, in addition to evaluating overall quality of life, can be used to assess 6 different aspects that may affect quality of life: symptoms and feelings, daily activities, leisure, work or school performance, personal relationships, and treatment. The DLQI is calculated by summing the score of each question resulting in a maximum of 30 and a minimum of 0. A higher score indicates more severe disease. A score of  $\leq 1$  indicates no effect at all of disease on subject's health related quality of life, and a reduction of 5 points or more in total DLQI score is considered clinically meaningful improvement.

For a partially answered questionnaire (eg, not all 10 answers in the DLQI questionnaire were available):

- If one question's answer is not available, this question will be scored 0. The total score will then be calculated.
- If two or more questions' answers are unavailable, the questionnaire is not scored. Hence, the total score and each of the 6 component scores will be set to missing.

If one question from one of the 6 component scores is missing, the affected component score will be set to be missing.

#### **5.4.5.2. Analyses Related to DLQI**

- The change from baseline in DLQI at Week 16 will be compared between each bermekimab group and placebo group using a MMRM model to test the difference between treatment groups.
- The proportions of participants with DLQI score of 0 and 1 at Week 16 for the participants with baseline DLQI score  $>1$  and the proportion of participants with a reduction of 5 or more points in DLQI score for the participants with baseline DLQI score  $\geq 5$  at Week 16 will be compared between each of the bermekimab groups and the placebo group.
- The change from baseline in DLQI total score will be summarized over time by treatment group.
- The proportions of participants with DLQI score of 0 and 1 for the participants with baseline DLQI score  $>1$  and the proportion of participants with a reduction of 5 or more points in DLQI score for the participants with baseline DLQI score  $\geq 5$  will be summarized by treatment group over time.
- The change from baseline in each DLQI component score will be summarized by treatment at Week 16.

#### **5.4.6. Hospital Anxiety Depression Scale (HADS)**

##### **5.4.6.1. Definition**

The HADS is an instrument for screening anxiety and depression in non-psychiatric populations; repeated administration also provides information about changes to a patient's emotional state. The HADS consists of 14 items, 7 each for anxiety and depression symptoms; Each item on the questionnaire is scored from 0-3 resulting in a score between 0 and 21 for either anxiety or depression. The following cut-off scores are recommended for both subscales: 7 to 8 for possible presence, 10 to 11 for probable presence, and 14 to 15 for severe anxiety or depression. The HADS is provided in the study reference manual.

If one or more of the items within each domain are left unanswered, that HADS component score will be considered missing.

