### **5.2.2. Data Handling Rules**

No imputation will be performed for missing baseline values.

For the main analysis of primary endpoint of EASI-75 response at Week 16, a subject who discontinued treatment will be considered as a non-responder from that point onward. The remaining missing data will be imputed as non-responder. Supplementary analyses will be performed and include (1) using observed data regardless of whether the subject discontinued treatment or have missing data, and (2) data after treatment discontinuation will be considered as missing, missing response will be imputed by multiple imputation methods under the assumption of missing at random. Similar data handling rules (i.e., main analysis with non-responder imputation and 2 supplementary analyses) will also be applied for EASI-75 response over time through Week 16. The following data handling rules will be applied for other endpoints:

Binary secondary endpoints:

- Analyses will be similar to the main analysis of the primary endpoint. A subject who discontinued treatment will be considered as a non-responder from that point onward. The remaining missing data will be imputed as non-responder. Supplementary analyses will be performed for selected endpoint (i.e IGA responses) in the same manner as the primary endpoint.

Continuous secondary endpoints:

- If a subject discontinued treatment, zero will be assigned to improvement or percent improvement. Remaining missing data will not be imputed. A MMRM model will adjust for missing post baseline data and all available data from the 3 treatment groups through Week 16 or from Week 16 through Week 36 will be included. Under the assumption of missing at random (MAR), the missing data will be accounted for through correlation of repeated measures in the model. Supplementary analyses will be performed for selected endpoints (i.e. EASI total score, NRS itch score) and include (1) using observed data regardless of whether the subject discontinued treatment or have missing data, and (2) data after treatment discontinuation will be considered as missing, missing data will be addressed by MMRM model.

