### **5.4.6.2. Analyses Related to HADS**

- The improvement from baseline in Hospital Anxiety and Depression scale at Week 16 will be compared between each of the bermekimab groups and placebo group using a MMRM model.
- The proportion of participants with hospital anxiety scale  $<8$  and depression scale  $<8$  at Week 16 will be compared between each of the bermekimab groups and placebo groups among participants with a baseline hospital anxiety scale and depression scale  $\geq 8$ .
- Hospital anxiety scale and depression scale shift from baseline to Week 16 with respect to the hospital anxiety and depression scale category ( $<8$ ,  $\geq 8$ ) will be summarized.
- The improvement from baseline in Hospital Anxiety and Depression Scale will be summarized by treatment group over time.

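### One skipped HADS item voids the seven-item subscale, so the Week 16 HADS <8 analysis can code as failures patients whose answered items already prove a score below 8

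*SAP*

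**What the plan says.** **HADS scoring (SAP 5.4.6.1).** The anxiety and depression subscales have seven items apiece. On the scoring of items the SAP states: "Each item on the questionnaire is scored from 0-3 resulting in a score between 0 and 21 for either anxiety or depression". The missing-item rule is: "If one or more of the items within each domain are left unanswered, that HADS component score will be considered missing".

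**HADS analyses (SAP 5.4.6.2).** Improvement in each scale at Week 16 is compared by MMRM. Separately, each bermekimab arm is set against placebo on the proportion scoring below 8 at that visit. This comparison is made "among participants with a baseline hospital anxiety scale and depression scale" of at least 8. A shift table uses the same two categories.

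**Missing data (SAP 5.2.2, applied to secondary endpoints by 5.4 and 5.4.1).** For baseline: "No imputation will be performed for missing baseline values". For binary secondary endpoints after baseline: "The remaining missing data will be imputed as non-responder". For continuous endpoints, missing values in patients still on treatment are left to the MMRM under missing at random. Nothing overrides these rules for HADS.

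**Baseline.** SAP 2.7 takes the closest measurement at or before first dose. Protocol 8.1 takes the Week 0 pre-injection assessment. HADS is collected at both screening and Week 0 (protocol 5.2).

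**DLQI (SAP 5.4.5.1).** With one of ten answers missing, that item is scored 0 and "The total score will then be calculated". A DLQI component score with a missing item is set to missing.

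**The concern.** Non-responder imputation is a convention for an outcome that is not known. Here the scoring rule discards six recorded answers out of seven and declares the outcome unknown, even when those six answers settle it. A patient still on treatment who attends Week 16, completes almost all of the form and has very low scores is then reported as still at or above the cut-off of 8. The shift table loses the same patient.

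The analysis is restricted to patients with baseline ≥8, so it uses fewer than the roughly 30 per arm randomised (90/3), and each miscoded patient moves the proportion more. The rule also removes usable scores from the MMRM for the HADS change endpoints.

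**Working it through.** **1. The plan's own figure.** 7 items × 3 points = 21, which matches the stated 0 to 21 range.

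**2. What one missing item leaves uncertain.** Let S be the sum of the six answered items. The full score lies between S and S + 3.

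| S | Possible full score | Status against 8 | SAP coding at Week 16 | 7/6 × S |
|---|---|---|---|---|
| 0 to 4 | at most 7 | certainly <8 | failure (wrong) | at most 4.67: <8 |
| 5 | 5 to 8 | undetermined | failure | 5.83: <8 |
| 6 | 6 to 9 | undetermined | failure | 7.00: <8 |
| 7 | 7 to 10 | undetermined | failure | 8.17: ≥8 |
| 8 or more | at least 8 | certainly ≥8 | failure (right) | at least 9.33: ≥8 |

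The 7/6 score is never wrong outside S = 5 to 7. Within that band it errs if the missing item is 3 (S = 5), 2 or 3 (S = 6), or 0 (S = 7). With two items missing, only S of 0 or 1 guarantees <8 (1 + 6 = 7).

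**3. How often a subscale is lost.** The documents give no skip rate, so q per item is assumed, with skips independent. Any of seven missing: 1 − (1 − q)^7. Exactly one missing: 7q(1 − q)^6. Per 30 patients: 30 times the first.

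| q (assumed) | Subscale lost per visit | Exactly one item missing | Lost per 30 patients | Lost if one missing item is tolerated |
|---|---|---|---|---|
| 0.25% | 1.7% | 1.72% | 0.5 | 0.01% |
| 0.5% | 3.4% | 3.40% | 1.0 | 0.05% |
| 1% | 6.8% | 6.59% | 2.0 | 0.2% |
| 2% | 13.2% | 12.40% | 4.0 | 0.8% |

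A single missing item accounts for 94% to 99% of the losses (12.40/13.19 at q = 2%; 1.72/1.74 at q = 0.25%).

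**4. Expected miscoding in the <8 analysis, per arm and per subscale.** The documents give neither the number with baseline ≥8 nor the response rate. Simulation of seven correlated 0 to 3 items (assumed baseline mean 2.6 to 5.4) put 7% to 29% of patients at or above 8, that is 2 to 9 of 30. Take 9 eligible, 80% truly <8 at Week 16, and 84% of those with S ≤ 4 when one item is missing:

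9 × 0.80 × 0.84 = 6.05 patients exposed to a provably wrong code.

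- q = 0.25%: 6.05 × 0.0172 = 0.10
- q = 0.5%: 6.05 × 0.0340 = 0.21
- q = 1%: 6.05 × 0.0659 = 0.40
- q = 2%: 6.05 × 0.1240 = 0.75

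The 84% is itself assumed. Simulations restricted to baseline ≥8 gave about 60% to 79% with no mean change between visits and 71% to 86% under other assumed score distributions. As a ceiling, if all 30 patients in an arm were eligible, q = 2% would give 30 × 0.80 × 0.84 × 0.1240 = 2.5.

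**5. Precision of the change endpoints.** If the MMRM recovered nothing, losing Week 16 alone would widen an interval by 1/√(1 − loss) − 1: 0.9%, 1.8%, 3.6% and 7.3% for the four values of q. HADS is also taken at Weeks 1, 2, 4, 6, 8 and 12 (protocol 5.2.1), so the real cost is smaller.

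**The case against.** **The rule is explicit, prespecified and the same in every arm.** This is true, and it answers any charge of ambiguity or arm-specific handling. It does not make a failure code correct when the recorded answers rule failure out.

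**A skipped baseline item need not remove the patient.** A reader might infer that it always does, because missing baselines are not imputed. The documents do not support that. SAP 2.7 could let a complete screening HADS serve. The patient is lost only if no complete screening score may be used, and protocol 8.1, which names Week 0 only, leaves that open.

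**The protocol's HADS endpoints are not coded as failures.** The eight protocol secondary endpoints (two subscales at four weeks) are all changes from baseline. Failure coding reaches only the <8 comparison that the SAP adds.

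**The DLQI contrast is partial.** A reader might infer that the SAP is lenient with DLQI and strict with HADS throughout. Only the DLQI total tolerates a missing item. DLQI component scores are as strict as the HADS subscales, which the SAP also calls component scores. The DLQI total sets the missing item to 0, so it is no precedent for prorating.

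**Prorating also errs.** Six items summing to 6 with a true seventh answer of 2 total 8, yet prorate to 7.0. This stands, but is confined to S = 5 to 7. Assigning the category only where it is already determined avoids it.

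**The numbers are assumed.** This stands too: every frequency above depends on a skip rate and score distribution that the documents do not give.

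**Conclusion.** The point holds for the Week 16 HADS <8 analysis: with six answered items summing to 4 or less, the SAP's rules produce a provably wrong code. That part is arithmetic and needs no assumption. For the change endpoints, a post-baseline loss is only a modest loss of precision, on the SAP's own missing-at-random assumption.

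The practical effect is small. Over assumed skip rates of 0.25% to 2%, the expected number provably miscoded is about 0.1 to 0.75 per arm and subscale with 9 eligible patients, and fewer if fewer qualify. A reader might infer a bias large enough to alter the trial's conclusions; the documents do not support that. The primary endpoint, sample size and type I error are untouched, and p-values for secondary analyses are nominal (SAP 5.2.1 and 5.4). This is a cheap improvement that is worth making but not essential.

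**What to change.** In SAP 5.4.6.1, replace the missing-item rule with: if exactly one of the seven items of a subscale is missing, score the subscale as 7/6 times the sum of the six answered items, without rounding; if two or more are missing, set it to missing. Apply this at baseline and after baseline.

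At a minimum, for the <8/≥8 responder analysis and shift table, assign the category whenever the answered items already determine it (with one item missing, S ≤ 4 or S ≥ 8), and leave the other cases under the present rules. This needs no imputation assumption.

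Also state whether a complete screening HADS may serve as baseline when the Week 0 form is incomplete, so that SAP 2.7 and protocol 8.1 agree. SAP 5.4.6.1 refers to a study reference manual for the HADS; check that any scoring instruction there is consistent with the rule adopted.

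The cost is one sentence and a change to the scoring code, settled before unblinded HADS data are seen. The downside of prorating is a small single-item imputation assumption, with occasional misclassification for six-item sums of 5 to 7.

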### **5.4.6.2. Analyses Related to HADS**

- The improvement from baseline in Hospital Anxiety and Depression scale at Week 16 will be compared between each of the bermekimab groups and placebo group using a MMRM model.
- The proportion of participants with hospital anxiety scale  $<8$  and depression scale  $<8$  at Week 16 will be compared between each of the bermekimab groups and placebo groups among participants with a baseline hospital anxiety scale and depression scale  $\geq 8$ .
- Hospital anxiety scale and depression scale shift from baseline to Week 16 with respect to the hospital anxiety and depression scale category ( $<8$ ,  $\geq 8$ ) will be summarized.
- The improvement from baseline in Hospital Anxiety and Depression Scale will be summarized by treatment group over time.

### **5.4.7. Patient Oriented Eczema Measure (POEM)**

#### **5.4.7.1. Definition**

The POEM is a 7-item, validated questionnaire used in clinical practice and clinical trials to assess disease symptoms in children and adults. The format is a response to 7 items (dryness, itching, flaking, cracking, sleep loss, bleeding, and weeping) based on frequency during the past week (ie, 0 = no days, 1 = 1 to 2 days, 2 = 3 to 4 days, 3 = 5 to 6 days, and 4 = all days) with a scoring system of 0 to 28; the total score reflects disease-related morbidity. The POEM is provided in the study reference manual.

#### **5.4.7.2. Analysis Methods**

- The change from baseline in POEM total score at Week 16 will be compared between each of the bermekimab groups and placebo group using a MMRM model.
- The change from baseline in POEM total score will be summarized by treatment group over time.
- The change from baseline in each POEM component score will be summarized by treatment group at Week 16.

### **5.4.8. SCORing Atopic Dermatitis (SCORAD)**

#### **5.4.8.1. Definition**

The SCORAD is a validated tool used in clinical research and clinical practice that was developed to standardize the evaluation of the extent and severity of AD. There are 3 components to the assessment: A = extent or affected body surface area, B = severity, and C = subjective symptoms. The extent of AD is assessed as a percentage of each defined body area, and reported as the sum

of all areas, with a maximum score of 100% (assigned as “A” in the overall SCORAD calculation). The severity of 6 specific symptoms of AD (redness, swelling, oozing/crusting, excoriation, skin thickening/ lichenification, dryness) is assessed using the following scale: none (0), mild (1), moderate (2), or severe (3) (for a maximum of 18 total points, assigned as “B” in the overall SCORAD calculation). Subjective assessment of itch and sleeplessness is recorded for each symptom by the patient or relative on a VAS, where 0 is no itch (or sleeplessness) and 10 is the worst imaginable itch (or sleeplessness), with a maximum possible score of 20. This parameter is assigned as “C” in the overall SCORAD calculation. The SCORAD is calculated as:  $A/5 + 7B/2 + C$  where the maximum is 103. A higher score indicates more severe disease.

Body surface area (BSA) affected by AD will be assessed for each section of the body (the possible highest score for each region is: head and neck [9%], anterior trunk [18%], back [18%], upper limbs [18%], lower limbs [36%], and genitals [1%]) and will be reported as a percentage of all major body sections combined. Body Surface Area will be extracted using SCORAD.

